### Secondary dataset

- 4,999 reported stands, 0 falls
- Variables included – event type, start date, stop date, room, unit, bed, seconds. We used the fall data for the primary outcome of estimating the fall rate and the length of each stand event to summarize the average time of stands.

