	
Android tablet (IRT), a nurse station Android monitor (HUC), a local server (PLS), a cloud server (PCS), a Bluetooth Low Energy beacon(s), an Android smart notification device, and an e-textile sock connected sensor transmitter (PUP™ sock).
 
The PUP™ sock monitors and transmits pressure, force, acceleration and motion data to IRT and PLS, and HUC and PCS. This data is evaluated and validated by an Android application on the IRT to determine whether or not a fall risk patient is standing unaccompanied by a caregiver. If a monitored patient is standing unattended, the PLS locates and alerts the Smart Notification Devices of the five (5) closest healthcare providers and the HUC using the beacon technology.
 
Alerts are terminated by the Smart Notification Device and PLS based on caregiver proximity to the patient. All data, alerts, suspensions, terminations and notifications are recorded by the PCS. On a daily basis, PCS reports are produced which contain data for each patient enrolled, number of alerts, excessive alerts, and caregiver response time, as well as summaries by Pod and entire facility.
 
All Brain and Spine Hospital patients will be evaluated as to fall risk using the current fall risk assessment procedures employed by OSU Medical Center and administered in the usual and customary fashion upon evaluation on the floor and Pod.
 
Any patient fall is to be reported and evaluated following current processes and procedures developed by the OSU Brain and Spine Institute as maintained with IHIS.
 
If a fall risk patient is admitted to the unit and is not otherwise disqualified by the Study Exclusion Criteria, the patient and/or LAR in form of a Patient Consent document, will be given information about and the opportunity for the patient to participate in the Study. If the patient or legal surrogate declines participation, the patient will receive standard of care provided prior to the Study.
 
Upon receiving a consent to participate, the patient will be fitted with a monitored PUP™ sock sized to the patient's foot from the Study inventory, and thereafter enrolled by a caregiver in the Palarum Fall Prevention System using an Android application on the IRT. The Palarum Fall Prevention System and PUP™ sock thereafter monitor the patient's activity 24x7 throughout the patient's entire length of stay. During the patient's stay, the PUP™ sock will be evaluated daily for proper fit, patient comfort, and patient safety. Upon discharge or transfer, the patient is un-enrolled from the system again

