--	---

	
utilizing the IRT. All patient relevant fall data, including system performance, is collected and stored in the PCS for future study and evaluation. Any patient fall is to be reported and evaluated following current OSU Medical Center processes and procedures independent of the Palarum Fall Prevention System.
 
Technical support for the Palarum Fall Prevention system is available by phone at [name] [contact] and email, [contact], 24x7. If there is a Palarum Fall Prevention System outage each Intervention Group Pod should follow policies related to downtime procedures for fall risk patients.

CONTROL PRODUCT, DOSE AND ROUTE OF ADMINISTRATION	N/A
DURATION OF SUBJECT PARTICIPATION AND DURATION OF STUDY	Duration: Once a patient has been placed in the fall risk protocol, the patient will remain in the study until a nurse removes the patient from risk fall status or the participant has been discharged from the hospital.
CONCOMITANT MEDICATIONS	
Allowed: YES
 
Prohibited: NONE

EFFECTIVENESS EVALUATIONS	
Effectiveness evaluation data will be collected by the Palarum Fall Risk System, and incorporated and integrated with patient diagnosis, co-morbidities, and other medical data within REDCap including:
 
 1. Enrollment Data 
 a. Patient Identifier/MRN b. Patient Weight c. Patient Sock Size (S-M-L-XL) d. Sex e. Pod and Room/Bed f. Date g. Time h. Sock Number i. Sensor Number 2. Event Logs 3. Time of stand alert 4. Time to clear 5. Who cleared stand 6. Manual or Automatic termination 7. Accelerator and Gyroscopic Data surrounding each stand event

	8. Pressure on foot 9. Motion of patient
PRIMARY ENDPOINT	Fall rate per patient days within the study sample population
SECONDARY ENDPOINTS	
As collected by the Palarum Fall Prevention System, validated by manual audits of thereof, and integrated with REDCap,
 
 • Rate of false alerts • Rate of fall related patient safety events • Time to respond to alert • Pressure on foot • Motion of patient • Alert fatigue analyzed and measured by alert responded/alerts generated over time. • Notification system alerts only the closest five caregivers when a fall risk patient is up • Time to staff notification (latency) when a fall risk patient is up and unattended • Time to clear data • Identification of caregiver clearing alert • Determination of manual or automatic termination

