4 STUDY DESIGN

4.1 Study Overview

- **Problem** - Falls occur at a rate of 5.5 per 1000 patient days in US hospitals. In addition to the human morbidity and mortality costs, falls cost hospitals in excess of \$8 billion in unreimbursed charges. No intervention to date has been shown to significantly reduce that rate.
- **Purpose** - To determine the effectiveness, if any, of the PUP™ Fall Prevention System. The hypothesis is that the System will reduce the fall rate by at least 25% of prior years' average fall rate.
- **Population to be studied** - All fall risk patients, eighteen years old or older, admitted to OSU Brain and Spine Hospital on Floors 8, 9, and 10 until the sample size is reached.
- **Research Design** – Single arm trial
- **Extent of Researcher Interference** - Minimal, only studying events as they normally occur. The PUP™ System will have been previously evaluated and approved for use as the standard of care at the OSU Medical Center Brain and Spine Hospital in accordance with the terms of an agreement between Palarum and OSU Medical Center dated March 28, 2018.
- **Time horizon** - Current.
- **Study setting** - Non-contrived. OSU Medical Center Brain and Spine Hospital.
- **Measurement and measures**
 - Patient fall rate (measured as number of falls/1000 patient days) data collection and reporting forms, criteria and protocols for the three calendar years preceding initiation of the research.
 - Patient fall rate data collection and reporting forms, criteria, and protocols for the research period calendar year.
 - Data collection standards and protocol for/of;
 - Positive stand detection alert
 - Negative stand detection alert
 - Participant inclusion, exclusion or exemption
 - Sampling methods of 1-3 above
 - Report form(s), structure and content
 - Participant or data exclusion standards, if any.
- **Data Collection Method** - Unobtrusive automated physical measurement using the PUP™ sock, sensors, wireless technology, and REDCap.

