#### Study Objectives

- To determine if the fall rate (as measured by falls per 1000 patient days) for patients designated “high fall risk” decreases with the use of the intervention (Patient is Up fall prevention technology [PUP]) when compared to historical NDNQI data for the prior 12 months (“Benchmark Data”) from nursing units where the intervention is being undertaken.
  - We ran a one-sided one-sample test for Poisson means using fall events (0 falls) and length of stay (2211.6 days) to estimate the fall rate
  - Results are presented as the fall rate and the corresponding one-sided 90% confidence interval which provides an upper bound for the fall rate.
    - 0 falls (Upper bound 1.04) per 1000 days
  - This fall rate was lower than the historical rate of 4 falls per 1000 days
- To reduce the incidence of false alerts, <5%. Our goal is a high reliability notification system.
  - No data collected for this
- To provide positive alert reliability of 95%. Our goal is to reduce alert fatigue with nurses. To determine number of alerts sent out; what is the frequency of these patient safety events (i.e.), fall risk patient up, out of bed, unassisted
  - No data collected for this
- To gather compliance data and response times from alert to caregiver response.

- Stand Time captured in seconds

Variable	Level	Total (n=4999)
Stand (seconds)	Median (IQR) (min, max)	24.0 (5.0, 64.0) (1.0, 593.0)

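### The zero falls behind the primary result come from the Palarum event file; the SAP does not say how falls enter it or whether it was checked against hospital fall reports

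*SAP*

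**What the plan says.** **SAP.** Under Palarum Data, the Secondary dataset section summarises the event file as "4,999 reported stands, 0 falls", lists its variables as "event type, start date, stop date, room, unit, bed, seconds", and says "We used the fall data for the primary outcome of estimating the fall rate". Under Study Objectives, the one-sided Poisson test was run "using fall events (0 falls) and length of stay (2211.6 days) to estimate the fall rate". The result is 0 falls per 1000 days with an upper bound of 1.04, described as lower than the historical 4 per 1000.

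**Protocol, hospital route.** The Method of Use text in the Synopsis says falls are reported and evaluated under "processes and procedures developed by the OSU Brain and Spine Institute as maintained with IHIS". It later adds: "Any patient fall is to be reported and evaluated following current OSU Medical Center processes and procedures independent of the Palarum Fall Prevention System".

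**Protocol, Palarum route.** The same Method of Use text says fall data on patients are gathered and held in the PCS, which is Palarum's cloud service. The Synopsis entry on effectiveness evaluations says "Effectiveness evaluation data will be collected by the Palarum Fall Risk System" and that these data are integrated in REDCap. Section 4.1 gives the collection method as automated measurement through the sock, sensors, wireless technology and REDCap. It also lists "Patient fall rate data collection and reporting forms, criteria, and protocols for the research period calendar year", without saying whether these forms are the hospital's or Palarum's.

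**The concern.** The primary result rests on one count from one file, and the SAP does not show that this file captures falls as the protocol defines them. The alerts and event logs described in Sections 4.2 and 9.3 concern stands: an alert follows a foot on the floor and a step, and the log records when and how it was cleared. The endpoint in Section 5.1 is wider. It counts assisted falls, fainting, and rolling from a low bed onto a mat. No described system function records any of these as a fall.

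The comparator is NDNQI data for the nursing units. If the study count comes from the device file alone, falls may be ascertained differently on the two sides of the comparison.

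The error could go only one way. A fall reported to the hospital but absent from the Palarum file lowers the observed rate and makes the device look better.

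**Working it through.** **1. What could verify the zero?**

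- SAP, Secondary dataset: no statement of how a fall is entered, whether by sensor, staff entry or merge from hospital reports.
- SAP, Falls Data (Ohio State): the only item is History of Falling, cut to the first entry per patient. A first entry cannot show what happened later in the stay.
- SAP, Data discrepancies: compares patient lists (58 in OSU only, 48 in Palarum only, 521 in common). It does not compare falls.

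Nothing the SAP describes checks the count.

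**2. Reproduce the SAP's figure.** Inputs: x = 0 falls and T = 2211.6 days (SAP, Study Objectives); historical rate 0.004 per day and alpha 0.1, one-sided (Protocol 13.2).

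- Upper bound for x = 0: -ln(0.1)/T = 2.3026/2211.6 = 0.001041, or 1.04 per 1000 days. This matches the SAP.
- Expected falls at the historical rate: 0.004 × 2211.6 = 8.85.
- One-sided p = P(X ≤ 0) = exp(-8.846) = 0.00014.

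**3. Vary the count.** Let x be the verified number of falls, with T held fixed. Then p = P(X ≤ x) for a Poisson mean of 8.846, and the upper bound is the 90th percentile of chi-square on 2(x+1) degrees of freedom, divided by 2T.

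| Falls | Rate per 1000 days | 90% upper bound per 1000 days | One-sided p |
|---|---|---|---|
| 0 | 0 | 1.04 | 0.00014 |
| 1 | 0.45 | 1.76 | 0.0014 |
| 2 | 0.90 | 2.41 | 0.0070 |
| 3 | 1.36 | 3.02 | 0.024 |
| 4 | 1.81 | 3.61 | 0.060 |
| 5 | 2.26 | 4.19 | 0.125 |

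The reported bound changes with the first omission. The decision at alpha 0.1 changes at the fifth. Five falls would be 5/8.846 = 57% of the number expected, and the rate of 2.26 would still be below 4.

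**4. How informative is a recorded zero?** Suppose the file captures a share c of falls (an assumption; the documents give no value) and the true rate is unchanged at 4 per 1000. The chance of recording none is exp(-8.846c):

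- c = 100%: 0.00014
- c = 50%: 0.012
- c = 25%: 0.11
- c = 10%: 0.41

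If capture is good, zero is strong evidence of a lower rate. If capture is poor, it is weak evidence. The SAP does not say which applies.

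**Limit of the check.** The SAP computes stay from first enrolment to last unenrolment after collapsing multiple entries, so 2211.6 days is not shown to be monitored time. The table takes that figure as given.

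**The case against.** The strongest reply is that the analyst used the source the protocol names. The protocol says fall data are held in the PCS and effectiveness data are collected by the Palarum system, and Section 4.1 describes automated collection with REDCap. The event file has an event-type variable, and a summary that reports stands and falls separately is consistent with a fall category. Hospital reports may already have been merged in.

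This reply largely stands against two stronger readings:

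- A reader might infer that the SAP departs from the protocol. The documents do not support that. The protocol requires hospital reporting of falls but orders no reconciliation, and its text allows falls to be taken from Palarum data.
- A reader might infer from the listed variables that the event file has no patient identifier and so cannot be matched. That does not follow either. The lists for the primary Palarum file and the OSU admission file name no identifier, yet those files were reduced to single patients and compared with each other.

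The reply does not supply the missing link. The effectiveness list in the Synopsis has no fall item, the case report form in Appendix C as shown has no fall field, and no passage says hospital reports were merged.

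A second reply is that the test is robust. That is true of the decision up to four unrecorded falls. It is not true of the published upper bound.

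**Conclusion.** The point holds as a gap in verification of the primary numerator. The SAP rests its only primary result on a file not shown to capture Section 5.1 falls, while the protocol already requires an independent hospital record that could confirm it.

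A reader might go further and conclude that falls were missed. The documents do not show this, and zero may be correct. The figures above say what omissions would do, not that any occurred.

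One unrecorded fall would raise the upper bound from 1.04 to 1.76 per 1000 days. Rejection at alpha 0.1 survives up to four and fails at five. These figures assume a Poisson count, the historical rate of 0.004, and 2211.6 days held fixed. The gap should be closed before the result is presented as a fall rate of zero.

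**What to change.** 1. State in the SAP how a fall enters the Palarum event file: sensor, staff entry, or merge from hospital reports.
2. Extract IHIS-reported falls that meet the Section 5.1 definition for all 569 Palarum patients, including the 48 with no OSU record, over the same time window as the denominator.
3. Reconcile the extract with the Palarum file event by event and list the discrepancies.
4. Take falls verified in either source as the primary numerator, then re-run the one-sided Poisson test and the 90% upper bound.
5. Until then, word the result as no falls recorded in the Palarum event file.

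If hospital reports were already merged, documenting the merge and its discrepancies is sufficient.

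The cost is one hospital extract, linkage work (mainly for the 48 patients), and an SAP wording change. The headline figure may become less favourable.

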## Ohio State Data

### Admission Data

- 895 entries with multiple admission times, locations and diagnoses
- 585 patients after limiting to first entry per patient
- Variables included – admission time, department, room, diagnosis, date, date of birth height, weight. From these we calculated age and BMI. Unit, department, and room information were not useful – these were not from 8, 9, or 10 East and South which was inclusion criteria.

Variable	Level	Total (n=585)
BMI	Mean (SD) (min, max)	missing=29 30.8 (8) (14.9, 59.7)
Age	Mean (SD) (min, max)	59.5 (16.8) (18.1, 102.6)

#### Falls Data

- 1,097 entries of “History of Falling” – repeated entries recorded on admission and every 8 hours
- 585 after reducing to first entry

Variable	Level	Total (n=585)
History of Falls	NULL	21 (4%)
	No	428 (73%)
	Yes	136 (23%)

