## Palarum Data

### Primary dataset

- 732 entries with multiple enrollment and unenrollment dates (technical error)
- 569 patients after data cleaning multiple entries by limiting data to first enrollment and last unenrollment
- Variables included – floor, unit, enrollment date, unenrollment date. From these we calculated length of stay.

Variable	Level	Total (n=569)
OSU unit	Missing	3 (1%)
	10 East	127 (22%)
	10 South	108 (19%)
	8 East	64 (11%)
	8 South	102 (18%)
	9 East	81 (14%)
	9 South	84 (15%)
Length of Stay (Days)	Median [IQR] (min, max)	2 [1, 3.9] (0, 127.2)

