#### Data discrepancies

- There were 58 patients in the OSU data that were not included in the Palarum data
- There were 48 patients in the Palarum data that were not included in the OSU data
- Total of 521 common patients between the 2 datasets

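### The hospital fall-history file has too few rows for the 8-hourly record the SAP describes, and the first-row rule keeps missing values without looking further

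*SAP*

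**What the plan says.** The SAP's Falls Data section reports "1,097 entries of" the hospital's fall-history item and describes them as "repeated entries recorded on admission and every 8 hours". It then keeps one row per patient, "585 after reducing to first entry", and tabulates NULL 21, No 428 and Yes 136. The Admission Data section treats its own file in the same way, "585 patients after limiting to first entry per patient", starting from 895 rows and ending with 29 missing BMI values. Neither section says what happens when the first row is empty, or whether the later rows were looked at.

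The stays come from the other source. The Primary dataset section starts from 732 device entries, attributes the multiple enrolment dates to a technical error, and arrives at "569 patients after data cleaning multiple entries by limiting data to first enrollment and last unenrollment". Stay has median 2 days, quartiles 1 and 3.9, and range 0 to 127.2. The Study Objectives section uses the total, 2211.6 days, as the denominator of the primary fall rate. The numerator comes from the device event file, which shows 0 falls (Secondary dataset: "We used the fall data for the primary outcome of estimating the fall rate"). The protocol synopsis, under Method of Use, wants falls reported through hospital processes independently of the device.

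The Data discrepancies section lists patients who fail to link between the two sources. It does not mention the fall-history row count.

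**The concern.** An item charted at admission and three times a day should leave many rows for a patient who stays several days. The file averages 1,097/585 = 1.88 rows per patient. If the charting description is right and the extract is whole, the stays must be too long, and the same stays are the exposure in the primary analysis. If the stays are right, the extract is incomplete or the charting is misdescribed, and the baseline table rests on a file whose content is not known.

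The reduction rule is a smaller matter. Taking the first row regardless of content scores a patient NULL even where a usable entry follows, and it removes all later rows without any described check. Protocol section 13.3 plans to look at fall rates by patient characteristics, so the coding of fall history has a planned, though exploratory, use.

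**Working it through.** **Reproducing the SAP's figures.** 21 + 428 + 136 = 585, giving 3.6%, 73.2% and 23.2%, as tabulated after rounding. The exact one-sided 90% Poisson upper limit for 0 falls is ln(10)/2211.6 = 2.3026/2211.6 = 1.04 per 1000 days, so 2211.6 days is indeed the exposure used.

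**Rows present.** 1,097 − 585 = 512 rows after the first (46.7% of the file). At one per 8 hours they cover 512 × 8/24 = 170.7 patient-days, or 7.7% of 2211.6.

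**Rows expected from the quartiles.** A quarter of the 569 device patients is 142. Give each quarter its shortest possible stay and count complete 8-hour intervals only: 0 days gives 0, 1 day gives 3, 2 days gives 6, and 3.9 days (93.6 h) gives 11. Add one first row for each of the 585 hospital patients.

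| Case | Calculation | Rows needed | 1,097 as a share |
|---|---|---|---|
| Upper two quarters only | 142×11 + 142×6 + 585 | 2,999 | 37% |
| Adding the second quarter | 2,999 + 142×3 | 3,425 | 32% |
| Upper two quarters, 48 unlinked patients assumed the longest stayers | 2,999 − 48×11 | 2,471 | 44% |
| Also discounting 163 stays entirely | 73×6 + 142×3 + 585 | 1,449 | 76% |
| Total exposure, for comparison | 3×2211.6 + 585 | 7,220 | 15% |

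The 48 is 569 less the 521 linked patients ("Total of 521 common patients between the 2 datasets"). The 163 is 732 − 569, the number of surplus device entries. At most 163 patients can have had a stay stretched by a gap between enrolments. The fourth row takes all 163 and all 48 from the upper half (2 × 142 − 163 − 48 = 73 left) and credits the 211 removed with no repeat rows at all. That is harsher than anything the documents suggest.

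Rounding does not close the gap. If the printed quartiles are rounded to one decimal, the shortest stays become 0.95 days (2 intervals) and 1.95 days (5 intervals). The fourth row then becomes 73×5 + 142×2 + 585 = 1,234, still above 1,097.

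**Missing values kept.** With 21 NULLs, the Yes share lies between 136/585 = 23.2% and (136 + 21)/585 = 26.8%. For BMI, 29/585 = 5.0% are missing after 895 − 585 = 310 rows were set aside. Recoverability cannot be read off. With 512 repeat rows, at least 585 − 512 = 73 patients have a single fall-history row, and all 21 NULLs could be among them. In the admission file at least 585 − 310 = 275 patients have a single row.

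**Conditional sensitivity of the primary result.** If falls were added to the count at 2211.6 days (expected under the benchmark: 0.004 × 2211.6 = 8.8):

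| Falls | Upper bound per 1000 days | One-sided p |
|---|---|---|
| 0 | 1.04 | 0.00014 |
| 1 | 1.76 | |
| 2 | 2.41 | |
| 4 | 3.61 | 0.060 |
| 5 | 4.19 | 0.125 |

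If instead the exposure were overstated and the count stayed at 0, the test at 0.1 would hold down to 2.3026/0.004 = 576 days, 26% of the figure used.

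**The case against.** The best defence of the rule is that a first entry is a normal choice for a baseline covariate. Fall history feeds one descriptive table and no reported test, and with 0 falls no association with fall rate can be estimated. That stands, and it limits the cleaning issue to a few percentage points in a baseline row. It is also fair that nobody can say the 21 NULLs or 29 BMIs were avoidable. The extra admission rows reflect multiple times, locations and diagnoses and need not carry height or weight.

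On the row count, the objection is that the quartile floor is not a true minimum, because stays running from first enrolment to last unenrolment may include gaps. This is right about the size of the shortfall: 2,999 is not a hard floor. It does not remove the contradiction, since 1,449 rows are needed even when every surplus device entry is allowed to cancel one long stay.

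Two stronger inferences are tempting. A reader might conclude that in-stay falls were recorded here as No-to-Yes changes and then deleted. The documents show no such change. They do not say the item is updated after an in-hospital fall, and a later Yes could be late capture of an older fall. All 512 dropped rows could repeat the first. A reader might also conclude that the file is only 15% complete, or that true exposure is nearer 171 days than 2,212. Each assumes one explanation of the mismatch. A change-only or date-limited extract would give the same count with the stays correct.

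**Conclusion.** The inconsistency between row count, charting interval and stays is real and unexplained in the SAP. At face value about 3,000 rows or more are needed; under the harshest discounting 1,449 (1,234 allowing for rounding); 1,097 are reported. This assumes that charting ran at least through device time in the linked patients, as the SAP's description implies. The cause is a partial extract, a wrong description, or overstated stays, and the documents do not settle which. Only the third would reach the primary result. With 0 falls, the comparison with the benchmark would survive unless about three quarters of the exposure disappeared, although the upper bound of 1.04 would rise with any reduction.

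The first-row rule is a minor weakness: 3.6% NULL fall histories, 5.0% missing BMIs, an unknown number recoverable, and effects confined to descriptive tables. It is not evidence of a missed fall. The figures for 1 to 5 falls show only how the result would move if hospital reports turned up events: still met with 4, lost with 5.

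**What to change.** 1. Query the row count against the stay lengths. According to the answer, re-extract the fall-history file, correct the statement of charting frequency, or correct the stays and with them the exposure denominator and upper bound.
2. Replace the first-row rule, for fall history and BMI, with the first non-missing entry of the study admission. Prefer entries up to device enrolment where that date exists, and otherwise take the earliest non-missing entry. The fallback is needed because 58 hospital patients are reported to have no device record and so no enrolment date. State how many values were recovered.
3. Before reducing the file, list any patient whose entry changes from No to Yes after device enrolment and check each against the hospital fall reports. This is a supplementary screen. It does not replace a direct check of the fall count against those reports.

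The cost is one data query, a few lines of code and one listing, plus one repeat extract if the present one proves partial. No new data collection is involved.
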